4.1.2 Hypotheses and Statistical Methods for Secondary Objectives

The superiority of the proportion of subjects with an RVNA titer ≥ 0.5 IU/mL at D28 to 95% will be tested only if the primary objective is demonstrated.

4.1.2.1 Hypotheses

If the primary objective is reached, the following hypotheses will be tested at D28, as part of the secondary objectives:

$H_0: P_{VRVg-2+HRIG} < 95\%$

$H_1: P_{VRVg-2+HRIG} \geq 95\%$

The proportion of subjects with an RVNA titer ≥ 0.5 IU/mL at D28 after receiving VRVg-2 will be considered as equal to or higher than 95% if the hypothesis H_0 is rejected.

4.1.2.2 Statistical Methods

The superiority testing will be demonstrated if the lower limit of the 95% CI of the proportion, calculated using the exact binomial distribution (1), is equal to or higher than 95%.

All other secondary endpoints will be described by vaccine group using descriptive statistical methods, as suggested in Table 5.1.

Immunogenicity endpoints

For all the subjects, a descriptive analysis for pre-Dose 1 (D0), 7 days post-Dose 3 (D14), 14 days post-Dose 4 (D28), and 14 days post-Dose 5 (D42) will present the following statistics for RVNA titers in each vaccine group:

- Number of subjects with RVNA titer available
- Number and percentage of subjects with RVNA titer ≥ 0.2 IU/mL (LLOQ) and 95% CI of the proportion
- Number and percentage of subjects with RVNA titer ≥ 0.5 IU/mL, and 95% CI of the proportion
- Number and percentage of subjects with complete or incomplete results at the starting dilution (1/5) of the RFFIT assay

- Among the analysis population
- Among the subset of subjects with a determined result (identical duplicate values, either Complete or Incomplete)
- GMTs and 95% CI of RVNA titers
- GM of individual titer ratio (GMTR) between the post vaccination time points (D14, D28, and D42) and the baseline (D0) within each group, and the 95% CIs:
 - D14/D0
 - D28/D0
 - D42/D0
- Distribution of titers (minimum, Q1, median, Q3, maximum): based on Log10 transformation first and then antilog transformation.
- Log₁₀ (Titer): mean and its standard deviation (SD)
- Reverse Cumulative Distribution Curves (RCDC) of RVNA titers at D0, D14, D28, and D42.

The complete descriptive immunogenicity data will be analyzed on the per-protocol analysis set (PPAS) primarily.

Safety endpoints

The analysis will be descriptive. The statistics presented in [Table 4.1](#) will be produced, based on the Safety Analysis Set (SafAS).

The safety analysis will report the occurrence of solicited reactions and the incidence of unsolicited AEs including SAEs and AESIs, over the safety observation period according to the vaccine received.

- Immediate unsolicited systemic AEs reported in the 30 minutes after each and vaccination.
- Solicited injection site reactions occurring within 7 days after each injection.
- Unsolicited injection site reactions occurring within 28 days after each injection.
- Solicited systemic reactions occurring between the first and the second injection, between the second and the third injection, and up to 7 days after the remaining injections.
- Unsolicited systemic AEs occurring between each injection and up to 28 days after the last injection.
- SAEs throughout the trial, ie, up to 6 months after the last injection.
- AESIs throughout the trial, ie, up to 6 months after the last injection.

In order to avoid any under-estimation of the incidences, the number of subjects with documented safety will be used as denominator of the frequencies.

- For solicited reactions, the denominator is the total number of subjects who have non-missing data for the particular category of reaction during the time period concerned.
Note: for solicited systemic reactions, if a reaction is ongoing at the time of the next vaccination, it will be treated differently depending on whether or not it has increased in intensity following the later vaccination.
 - If it has not increased in intensity after the next vaccination, it is to be attributed to the earlier vaccination, and is counted as just a single occurrence in safety analysis. The time of onset is the first day of the first occurrence in the earlier vaccination.
 - If it has increased in intensity after the next vaccination, it will be counted as 2 separate occurrences after each vaccination in safety analysis (the 2 occurrences will be attributed to the earlier vaccination and later vaccination, respectively). The date of the later vaccination will be considered as the end date for the first occurrence and the start date of the second occurrence, respectively.
- For unsolicited events, the denominator is the total number of subjects who were vaccinated at the dose analyzed (for the analyses after each dose) or the total number of subjects who were vaccinated at least one dose (for the analyses after any dose).

For safety parameters, 95% CIs of point estimates of proportion will be calculated using the exact binomial distribution (Clopper-Pearson method) for proportions [\(1\)](#).

30-minutes Post-Vaccination Observation Period

Unsolicited systemic AEs occurring within 30 minutes after each vaccination will be presented in summary safety tables, analyzed according to their causality (relationship to the study vaccine) and Grade 3 intensity.

Solicited Reactions

The solicited injection site reactions and the solicited systemic reactions will be presented according to the term listed in the eCRF, separately.

The solicited injection site reactions will be analyzed within 7 days after each vaccination (from D0 to D7), and within 7 days after any vaccination.

The solicited systemic reactions will be analyzed between each vaccination if vaccinations are separated less than 7 days, and up to 7 days after each vaccination if vaccinations are separated by 7 days or more.

Each type of solicited reactions will be presented after each injection according to:

- Maximum intensity during the solicited period and overall for on-going solicited reactions:

- Grade 1
- Grade 2
- Grade 3

- Time of onset categories are in [Table 4.2](#)

Table 4.2: Time of onset categories for solicited reactions

	Injection Site Reactions	Systemic Reactions
Post-Dose 1		D0-D3
Post-Dose 2	D0-D3 D4-D7	D0-D3
		D4
Post-Dose 3, 4, 5		D0-D3 D4-D7

- *Range of number of days of occurrence categories are in [Table 4.3](#)*

Table 4.3: Range of number of days of occurrence categories for solicited reactions during the solicited period

	Injection Site Reactions	Systemic Reactions
Post-Dose 1		1 - 3 days 4 days
Post-Dose 2	1 - 3 days 4 - 7 days 8 days	1 - 3 days 4 - 5 days
		1 - 3 days 4 - 7 days 8 days

- *Range of overall number of days of occurrence categories are in [Table 4.4](#)*

Table 4.4: Range of overall number of days of occurrence categories for solicited reactions during the solicited period

	Injection Site Reactions	Systemic Reactions
Post-Dose 1	1 - 3 days 4 - 7 days 8 days or more Missing end date	1 - 3 days 4 days 5 days or more Missing end date

Post-Dose 2	1 - 3 days 4 - 5 days 6 days or more Missing end date
Post-Dose 3, 4, 5	1 - 3 days 4 - 7 days 8 days or more Missing end date

- *Action Taken*

- Missing
- None
- Medication
- Healthcare provider contact
- Hospitalization
- Discontinuation of the study vaccination

Solicited reaction after any injection

“After any injection” means after all scheduled vaccine injections, and at least after the first vaccine injection (D0).

The solicited reaction will be presented after any injections according to:

- *Number of days of occurrence over the D0-D7 period for injection site reactions or between vaccinations for systemic reactions (up to D7 for the last 3 vaccinations)*
- *Time of onset period*
- *Intensity grade: the maximum intensity grade will be computed during the solicited period for all solicited reactions and overall for ongoing solicited reactions.*

Unsolicited Adverse Events

The unsolicited systemic AEs will be analyzed:

- “Between the first and the second vaccine injection”, which corresponds to AEs reported at V02 and occurring after the first vaccine injection^a

^a For subjects interrupting their vaccination schedule after the first injection, unsolicited AEs until 28 days after the first injection will be collected

- “Between the second and the third vaccine injection”, which corresponds to AEs reported at V03 and occurring after the second vaccine injection ^a
- “Between the third and the fourth vaccine injection”, which corresponds to AEs reported at V04 and occurring after the third vaccine injection ^b
- “Between the fourth and the fifth vaccine injection”, which corresponds to AEs reported at V05 and occurring after the fourth vaccine injection ^c
- “Within 28 days after the fifth vaccine injection”, which corresponds to AEs reported at V07 and occurring after the fifth vaccine injection
- “Within 28 days after any vaccine injection”, which corresponds to AEs belonging to any of the five above categories

The unsolicited injection site reactions will be analyzed within 28 days (from D0 to D28) after each vaccination, and within 28 days after any vaccination. An unsolicited injection site reaction (**excluding SAE and AESI**) reported with an onset > 28 days after a vaccination will not be included in the safety analysis, but will be listed separately.

The unsolicited systemic AEs will be analyzed between each vaccination if vaccinations are separated less than 28 days, or up to 28 days after each vaccination, if vaccinations are separated by 28 days or more or the next vaccination is interrupted, and up to 28 days after any vaccination. An unsolicited systemic AE (**excluding SAE and AESI**) reported with an onset > 28 days after vaccination will not be included in the safety analysis, but will be listed separately.

Note: An unsolicited AE with missing time of onset will be considered to have **occurred within or up to 28 days after the last vaccination** (computed according to [Section 3.3.1.2.3](#)), so will be included in safety analysis.

The unsolicited AEs will be summarized in the safety overview and analyzed according to their nature (SOC and PT of the MedDRA classification), causality (relationship to the study vaccine), time of onset, duration and maximum intensity.

The occurrence of any unsolicited AE will be presented after any and each injection according to:

- *Maximum intensity:*

- Missing
- Grade 1
- Grade 2
- Grade 3

^a For subjects interrupting their vaccination schedule after the second injection, unsolicited AEs until 28 days after the second injection will be collected

^b For subjects interrupting their vaccination schedule after the third injection, unsolicited AEs until 28 days after the third injection will be collected

^c For subjects interrupting their vaccination schedule after the fourth injection, unsolicited AEs until 28 days after the fourth injection will be collected

- *Time of onset categories:*

- Missing
- D0-D3
- D4-D7
- D8-D14
- $\geq D15$

- *Maximum duration:*

- Missing
- 1 - 3 days
- 4 - 7 days
- 8 - 14 days
- 15 days or more

SAEs and AESIs

In addition, the SAEs and AESIs, which are included in the unsolicited AEs, occurred during the study will also be analyzed on the following periods:

1. during vaccination period: from date of first vaccination (D0) to 28 days after the date of last exposure to study vaccine (date of last exposure + 28 days)
2. during the six-month safety follow-up period: from 29 days after the date of last exposure to study vaccine (date of last exposure + 29 days) to end of study (last visit date or contact date collected in eCRF)
3. during the study: from date of first vaccination (D0) to end of study [last visit date or contact date collected in eCRF])

SAEs will be analyzed according to their causality (relationship to the study vaccine), seriousness criteria, outcome and nature (SOC and PT of the MedDRA classification).

AESIs will be summarized and analyzed according to their nature (SOC and PT of the MedDRA classification) and causality.

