12.2.3 Per-Protocol Analysis Set

The Per-Protocol Analysis Set (PPAS) is a subset of the FAS.

As D28 is the time point used for primary objective assessment, the PPAS will be defined at D28 (V05). The subjects presenting with at least one of the following relevant protocol deviations before D28 (ie, 14 days after the fourth vaccine injection) will be excluded from the PPAS:

- Subject did not meet all protocol-specified inclusion criteria or met at least one of the protocol-specified exclusion criteria
- Subject did not receive the first 4 doses of the vaccination schedule
- Subject received a vaccine other than the one that he / she was randomized to receive
- Preparation and / or administration of vaccine (including HRIG for groups 1 to 3) was not done as per-protocol for the first 4 vaccinations
- Subject did not receive the first 4 vaccine injections in the proper time window
 - Vac2 in [D03-D05]
 - Vac3 in [D07-D09]
 - Vac4 in [D13-D16]

- Subject did not provide the post-dose 4 serology sample at V05 in the proper time window [D25-D31] from D0
- Subject received a protocol-prohibited therapy/medication/vaccine (belonging to categories 2 and 3) before V05
- Subject's serology sample is missing or did not produce valid test results at both D0 and D28
- Seropositive subject at D0, ie, RVNA titer \geq LLOQ
- Subject developed a protocol-specified withdrawal criterion during the study but was not withdrawn
- Subject did not receive the correct amount of HRIG at D0

Adherence to the definition of the PPAS analysis set may also be decided during the blinded data review, ie, before breaking the code and locking the data base.

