4.2.2 Per-Protocol Analysis Set

The PPAS is a subset of the FAS.

As D28 is the timepoint used for primary objective assessment, the PPAS will be defined at D28 (V05). The subjects presenting with at least one of the following relevant protocol deviations before D28 (ie, 14 days after the fourth vaccine injection) will be excluded from the PPAS:

- Subject did not meet all protocol-specified inclusion criteria or met at least one of the protocol-specified exclusion criteria
- Subject did not receive the first 4 doses of the vaccination schedule
- Subject received a vaccine other than the one that he / she was randomized to receive
- Preparation and / or administration of vaccine and concomitant medication (including HRIG for groups 1 to 3) was not done as per-protocol for the first 4 vaccinations
- Subject did not receive the first 4 vaccine injections in the proper time window
 - Vaccination 2 in [D03-D05]
 - Vaccination 3 in [D07-D09]
 - Vaccination 4 in [D13-D16]
- Subject did not provide the post-Dose 4 serology sample at V05 in the proper time window [D25-D31] from D0

- Subject received a protocol-prohibited therapy/medication/vaccine (belonging to categories 2 and 3) before V05
- Subject's serology sample is missing or did not produce valid test results at D0 or D28
- Seropositive subject at D0, ie, RVNA titer \geq LLOQ
- Subject developed a protocol-specified withdrawal criterion during the study but was not withdrawn
- Subject did not receive the correct amount of HRIG at D0

Adherence to the definition of the PPAS analysis set may also be decided during the blinded data review, ie, before breaking the code and locking the database.

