4.2.5 Populations Used in Analyses

The following table presents populations used in the statistical analysis.

Table 4.5: Populations used in the analyses

		Analysis sets	Analysis by
Primary Objective	D28 non-inferiority testing	PPAS (main analysis), FAS/FASI	Received vaccine group Randomized vaccine group
Secondary Objectives	D28 Superiority testing	PPAS (main analysis), FAS/FASI	Received vaccine group Randomized vaccine group
	Immunogenicity description	PPAS (main analysis), FAS/FASI	Received vaccine group Randomized vaccine group
	Safety description	SafAS	Received vaccine group
Exploratory analyses	Main immunogenicity endpoints	FASI (main analysis) PPAS*	Randomized vaccine group Received vaccine group
	Main safety endpoints	SafAS	Received vaccine group

*Note: Immunogenicity of subjects who did not take any concomitant medications for treating/preventing COVID-19 (ie, Hydroxychloroquine and chloroquine) within 2 months before enrollment

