4.6 Data Review for Statistical Purposes

A treatment blind review of the data has been anticipated through the data review process led by Data Management before database lock. This review of the data included a statistical review.

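### Does using a per-protocol set fixed at D28 for the D42 (post-dose-5) summaries call for a change?

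*SAP*

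**What the plan says.** SAP 4.2.2 gives its reason for the timing of the set: "As D28 is the timepoint used for primary objective assessment, the PPAS will be defined at D28 (V05". The list that follows covers deviations arising before D28. Protocol 12.2.3 has the same structure. The rules tied to a time all end at V05:

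- Doses: "Subject did not receive the first 4 doses of the vaccination schedule", with windows listed for vaccinations 2, 3 and 4.
- Sample: V05 serology within D25 to D31, and valid results at D0 and D28.
- Therapy: "Subject received a protocol-prohibited therapy/medication/vaccine (belonging to categories 2 and 3) before V05".

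Two provisions are less tightly tied to V05. One excludes a subject under the rule "Subject developed a protocol-specified withdrawal criterion during the study but was not withdrawn". The other is discretionary: "Adherence to the definition of the PPAS analysis set may also be decided during the blinded data review". SAP 4.6 adds that "This review of the data included a statistical review".

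For the description of the immune response, SAP Table 4.5 lists "PPAS (main analysis), FAS/FASI". Protocol Table 12.1 names the same sets for that row but does not rank them. SAP 4.1.2.2 includes D42 and the D42/D0 ratio among these summaries, and states: "The complete descriptive immunogenicity data will be analyzed on the per-protocol analysis set (PPAS) primarily".

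**The concern.** Secondary immunogenicity objective 2 describes, among other things, the response 14 days after the last vaccine injection, and D42 is the only sample taken after dose 5. A reader of a D42 table headed per-protocol would expect every contributing subject to have had five doses and a sample at the right time. As written, three kinds of subject could appear in it without that being true:

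1. No dose 5, but still bled near D42. At V05 the blood draw comes before the injection (Protocol 5.1.4), so a subject can meet every D28 rule and then have dose 5 withheld. Protocol 5.2.7.2 allows, without requiring, further immunogenicity follow-up after a definitive contraindication.
2. V06 sample outside 14 ± 3 days after dose 5.
3. Category 2 or 3 therapy, which Protocol 6.9 describes as possibly affecting the immune response, taken between V05 and V06.

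At stake is whether the D42 titers and response rates describe a five-dose response. No tested claim depends on it.

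**Working it through.** **What the text already catches.**

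- *Missed dose 5 or late V06.* Protocol 5.2.10 gives time-window failures and missed injections as examples of significant non-compliance, and 5.2.8 makes significant non-compliance, as judged by the investigator, a ground for automatic withdrawal. After early termination for an adverse event or a protocol deviation, 5.2.11 asks only for safety follow-up. Such a subject would then normally have no D42 sample. One who met the criterion and stayed in the study falls under the SAP's withdrawal-criterion exclusion.
- *Dose 5 timing.* Dose 5 is given at V05 after the D28 sample, and that sample must fall on D25 to D31. When dose 5 is given at that visit, its timing is therefore controlled indirectly.
- *V06 anchor.* The Table of Study Procedures and Protocol 5.1.4 already time V06 from dose 5. With dose 5 on D25 to D31, compliant samples run from 25 + 14 - 3 = D36 to 31 + 14 + 3 = D48. The D42 ± 3 label (D39 to D45) is marked as indicative.
- *The two holds.* The 71 and 29 hold subjects are expected to leave the PPAS. The 3 subjects who had finished vaccination at the COVID-19 stop had no later blood sample (Protocol 5.4.1), so they are missing at D42 and cannot distort it.

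Therapy between V05 and V06 is the clearest case with no rule of its own.

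**Size.** The planned evaluable numbers are 213 in Group 1 and 71 in each control group (SAP 4.5). They reproduce: Farrington-Manning power at 99% in both arms, margin 5% and one-sided 2.5% is 90.1% per comparison. A simple product gives 0.901 × 0.901 = 81.2% for both, against the stated 90% and 80%.

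If a share f of a group's D42 data has titers r times the rest, the geometric mean titer (GMT) is multiplied by r^f. The values of r and f are assumptions.

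| Affected share f | r = 1 | r = 0.5 | r = 0.25 |
|---|---|---|---|
| 1 of 71 | 0 | -0.97% | -1.93% |
| 1 of 213 | 0 | -0.32% | -0.65% |
| 5% | 0 | -3.41% | -6.70% |

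The 95% CI of a GMT, relative to its estimate, is 10^(± t × SD/√n). The log10 SD is assumed to be 0.3 to 0.5.

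| n | SD 0.3 | SD 0.5 |
|---|---|---|
| 71 | -15.1% / +17.8% | -23.9% / +31.3% |
| 213 | -8.9% / +9.8% | -14.4% / +16.8% |

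To move a control GMT by the narrower lower half-width at r = 0.5, f must equal ln(1 - 0.151)/ln(0.5) = 0.236, and 0.236 × 71 ≈ 17 subjects. In Group 1, ln(1 - 0.089)/ln(0.5) = 0.134, and 0.134 × 213 ≈ 29 subjects.

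For the proportion at or above 0.5 IU/mL, suppose everyone else responds and the one affected subject does not. The exact (Clopper-Pearson) lower limits are:

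- 71/71 to 70/71: 94.94% to 92.40%, a fall of 1/71 = 1.4 points in the rate.
- 213/213 to 212/213: 98.28% to 97.41%, a fall of 1/213 = 0.5 points in the rate.

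No success criterion applies at D42. The 95% threshold is tested only at D28 and only in Group 1.

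**The case for a change.** The strongest opposing case is that the safeguards are not watertight. The withdrawal-criterion exclusion speaks of the whole study but sits under a heading limited to deviations before D28, so its reach is unclear. Significant non-compliance is for the investigator to judge, and a dose 5 properly withheld for a contraindication need not be called non-compliance. The blinded review may decide on PPAS adherence, but no D42 criterion is written for it. The FASI (the full analysis set for immunogenicity) does not help here, since it does not require dose 5 either. The SAP also picks out five-dose subjects for a safety overview (4.1.3.3) but not for D42 immunogenicity.

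These points stand as reading of the text. If a subject without dose 5 were bled at D39 to D45, with dose 4 on D13 to D16, the sample would fall 39 - 16 = 23 to 45 - 13 = 32 days after the last injection, which does not fit the label. That timing is hypothetical, because the plan sets no V06 anchor when dose 5 is missing. Getting there takes a chain: every D28 rule met, dose 5 withheld for a reason that does not already exclude the subject, no withdrawal, and an optional later bleed.

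What does not follow is that a different analysis set is needed. Using one set across D14, D28 and D42 keeps the base population the same between visits, and both documents state openly where it is fixed. FASI results are shown alongside, and the number with a titer is reported at each time point.

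**Conclusion.** The gap in wording is real, but no change to the plan follows. The D42 results are descriptive, the set is disclosed, and the primary non-inferiority comparisons and the 95% test at D28 do not use D42 data. One affected subject at half or a quarter of the usual titer moves a group GMT by 0.3% to 1.9%. At half titer, about 17 of 71 or 29 of 213 would be needed to match even the narrower sampling error. One extra non-responder costs 1.4 or 0.5 percentage points, against no criterion.

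This rests on assumed relative titers, SDs and responder counts, and on the number of affected subjects being small. The documents do not give that number. The judgment would weaken if many subjects had received Category 2 or 3 therapy in the two weeks or so between V05 and V06.

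Nor would a new set gain much. SAP version 1.1 (25 August 2021) records that the active phase was locked on 28 May 2021 and has been unblinded, so a D42-specific per-protocol set could not be pre-specified. An analyst can deal with what remains in ordinary reporting, by saying that the D42 tables use the D28-defined PPAS and listing later deviations among contributing subjects.
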